9.1.1 Screening

Surgical Subjects

Assessments from screening through admission (pre-procedure) are listed in Table 3-1.

The Screening Visit will occur within 28 days before the scheduled surgical procedure and may occur in the clinic or as a home health visit with a qualified visiting nurse if permitted by local regulations. The investigator (or an appropriate authorized designee at the study site) will obtain informed consent from each subject in person or remotely (Section 13.2.3) before performing any study-related procedure. If needed, Screening Visit assessments may be performed on different days within the screening period (e.g., informed consent may be obtained before the home health visit, if applicable).

Non-surgical Subjects

Assessments from screening through treatment assigned are listed in Table 3-3.

The Screening Visit will occur on Day 1 after the subject presents with pain at a medical facility. The investigator (or an appropriate authorized designee at the study site) will obtain informed consent from each subject before performing any study-related procedure. However, previous test results from the facility's local laboratory may be used to establish eligibility if collected within 2 hours before ICF signing. All screening assessments must be completed, confirming

subject eligibility, before treatment assignment may occur, including VRS and (if the subject's pain is rated moderate or severe on the VRS) NPRS.

All Subjects

To prepare for study participation, subjects will be instructed on the study restrictions (Section 9.4).

Subjects will be instructed during screening on appropriate expectations around their participation in a clinical study and the importance of accurately reporting their post-procedural pain. At the Screening Visit, subjects will receive trainings on accurate pain reporting, clinical study participation, and use of the electronic diary (e-diary) for recording study drug administration, rescue medication use, and the PGA. On Day 1 (pre-procedure), these trainings will be repeated for surgical subjects; for non-surgical subjects, only 1 training is required because the Screening Visit is on Day 1. Additional review of these educational materials may be repeated for some or all subjects, as needed.

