11.5.2 Clinical Laboratory Assessments

Blood and urine samples will be analyzed at a central laboratory, unless otherwise specified.

Laboratory test results that are abnormal and considered clinically significant will be reported as AEs (see Section 11.5.1).

The safety laboratory test panels are shown in Table 11-1.

Serum Chemistry	Hematology	Urinalysis ^a
Glucose	Hemoglobin	Urobilinogen
Blood urea nitrogen ^b	Platelets	Urine protein
Creatinine	Leukocytes	pH
Sodium	Differential (percent):	Urine blood
Potassium	Eosinophils	Specific gravity
Calcium	Basophils	Urine ketones
Chloride	Neutrophils	Urine bilirubin
Magnesium	Lymphocytes	Urine glucose
Bicarbonate	Monocytes	
Phosphate	Coagulation	
Total bilirubin, direct bilirubin	Activated partial thromboplastin time	
Alkaline phosphatase	Prothrombin time	
Aspartate transaminase	Prothrombin time International	
Alanine transaminase	Normalized Ratio	
Amylase		
Lipase		
Gamma-glutamyl transferase		
Protein		
Albumin		
Creatine kinase		
Urate		

Table 11-1Safety Laboratory Test Panels

^a If urinalysis results are positive for protein or blood, microscopic examination of urine will be done, and results will be provided for leukocytes, erythrocytes, crystals, bacteria, and casts.

^b If blood urea nitrogen cannot be collected, urea may be substituted.

Clinical laboratory assessments during screening must have no clinically significant findings that preclude participation in the study, as judged by the investigator, for a subject to receive study drug on Day 1. For non-surgical subjects, local laboratory results will be used during screening; previous test results from the facility's local laboratory may be used to establish eligibility if collected within 2 hours before ICF signing.

Additional Screening Tests: The following additional tests will be performed at the Screening Visit and/or pre-procedure to assess eligibility:

- Serology (surgical subjects only): Hepatitis B surface antigen (HBsAg), hepatitis C virus antibody (HCV Ab), HCV RNA, and antibodies against human immunodeficiency viruses 1 and 2 (HIV-1/HIV-2 Abs). Subjects with detectable viral load will be excluded (Section 8.2).
- Serum Follicle-stimulating Hormone (FSH): Serum FSH will be tested at the Screening Visit for female subjects who are suspected to be postmenopausal (as defined in Section 11.5.6.1). For a subject to be considered of non-childbearing potential, the serum FSH levels will be

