within the laboratory range for postmenopausal females. For non-surgical subjects, a test result is not required for eligibility; however, until the test result is received, a subject will be considered to be of childbearing potential and must follow contraception requirements (Section 11.5.6.1) until postmenopausal status is confirmed.

- Pregnancy Testing: Surgical subjects: All biologically female subjects will have a serum beta-human chorionic gonadotropin (β-hCG) test during the Screening Visit. Female subjects of childbearing potential (Section 11.5.6.1) will also have a urine β-hCG test before admission on Day 1. Both the serum and urine β-hCG test must be negative to receive study drug. Non-surgical subjects: All biologically female subjects will have a urine β-hCG test during the Screening Visit, which occurs on Day 1; the test must be negative to receive study drug.
- Drug and Alcohol Screening: Drug screening for opioids, methadone, cannabinoids, cocaine, amphetamines/methamphetamines, barbiturates, and benzodiazepines will be assessed by a urine test at the Screening Visit and before admission on Day 1; for non-surgical subjects, only 1 test is required because the Screening Visit is on Day 1. Alcohol screening will be assessed before admission (surgical subjects) or treatment assignment (non-surgical subjects) on Day 1 by a urine, blood, or breath test. Subjects may undergo random urine drug screen and alcohol testing if deemed appropriate by the investigator. Drug and alcohol screen results must be negative for a subject to receive study drug; a positive marijuana screen will only be exclusionary on Day 1. A positive drug screen for a known prescribed concomitant medication that is not otherwise exclusionary (e.g., benzodiazepines) will not disqualify subjects.

Additional Evaluations: Additional clinical laboratory evaluations will be performed at other times if judged to be clinically appropriate.

For purposes of study conduct, only laboratory tests done in the central laboratory may be used, with the following exceptions:

- Day 1 (pre-procedure, if applicable) drug and alcohol tests and urine β -hCG pregnancy tests will be assessed by staff onsite.
- For **non-surgical subjects**, local laboratories will be used for safety laboratory tests at screening.

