9 STATISTICAL ANALYSIS

9.1 General Considerations

The Schedule of Assessments is provided in Section 3 of the CSP. The precision standards for reporting variables are provided in an internal Biometrics document that specifies the programming rules including the precision for derived variables.

All individual subject data for subjects who have received at least 1 dose of study drug will be presented in individual subject data listings.

Continuous variables will be summarized using the following descriptive summary statistics: the number of subjects (n), mean, standard deviation (SD), median, minimum value (min), and maximum value (max).

Categorical variables will be summarized using counts and percentages.

Baseline value, unless specified otherwise, will be defined as the most recent non-missing measurement (scheduled or unscheduled) collected before the first dose of study drug.

For ECGs, the baseline value will be defined as the average of the most recent non-missing measurements (scheduled or unscheduled) collected before the first dose of study drug, expected to be the triplicate predose measurements on Day 1.

Change (absolute change) from baseline will be calculated as post-baseline value – baseline value.

Treatment-emergent (TE) Period will include the time from the first dose of study drug to the Safety Follow-up Visit or to the completion of study participation (as defined in Section 9.1.7 of the CSP), whichever occurs first.

Unscheduled visits: Unscheduled visit measurements will be included in the analysis as follows:

• In scheduled visit windows per specified visit windowing rules

- In the derivation of baseline
- In the derivation of maximum and minimum values during the TE period, and maximum and minimum change from baseline values during the TE period for safety analyses
- In individual subject data listings as appropriate

Visit windowing rules: The analysis visit windows for protocol-defined PGA entries, which are provided by the subject in a dosing diary, are provided in Appendix A. All safety assessments are analyzed according to their nominal visits.

Outliers: No formal statistical analyses will be performed to detect and/or remedy the presence of statistical outliers.

Multiplicity: Only descriptive analyses will be performed; no statistical hypothesis testing will be performed.

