9.4.2 Clinical Laboratory Assessments

All statistical analyses of laboratory values will be performed using SI units. For treatmentemergent laboratory measurements, the observed values and change from baseline values of the continuous hematology, chemistry, and coagulation results will be summarized at each visit.

The number and percentage of subjects with selected test values meeting threshold analysis criteria during the TE period will be summarized. The number and percentage of subjects with shift from baseline in selected test values meeting threshold analysis criteria will also be summarized for chemistry measurements. The threshold analysis criteria are provided in Appendix D.

Results of urinalysis and the urine/serum pregnancy test will be in individual subject data listings only.

In addition, listings of individual subject hematology, chemistry, and coagulation values outside the normal reference ranges will be provided. These listings will include data from both scheduled and unscheduled visits.

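### For non-surgical subjects the scheduled laboratory baseline is local and the scheduled post-dose results are central, so change-from-baseline summaries mix laboratory differences with change on treatment

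*Protocol*

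**What the plan says.** Protocol 11.5.2 makes the central laboratory the default: "Blood and urine samples will be analyzed at a central laboratory, unless otherwise specified". It then tightens this for study conduct: "only laboratory tests done in the central laboratory may be used, with the following exceptions". One listed exception concerns non-surgical subjects, for whom "local laboratories will be used for safety laboratory tests at screening". The same section states the rule a second time ("For non-surgical subjects, local laboratory results will be used during screening"), and Table 3-3 repeats it.

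Protocol 9.1.1 fixes the timing for these subjects: "The Screening Visit will occur on Day 1 after the subject presents with pain at a medical facility".

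SAP 9.1 says that the baseline value "will be defined as the most recent non-missing measurement (scheduled or unscheduled) collected before the first dose of study drug", with no condition on which laboratory produced it. SAP 9.4.2 then plans that "the observed values and change from baseline values of the continuous hematology, chemistry, and coagulation results will be summarized at each visit". It also plans shift tables for chemistry against the Appendix D criteria. All laboratory analyses are to be in SI units. The SAP does not mention local versus central results, and Table 12-3 does not say whose reference limits apply.

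**The concern.** A change from baseline is easiest to read when both values come from the same method and calibration. Here the plan subtracts a local result from a central one for one group of subjects, and converting to SI units does not align assays. Any systematic difference between the two laboratories passes into the change as if it had happened on treatment, or offsets a change that did happen.

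Laboratory results are a named part of the primary endpoint, and there is no control arm in which the same artifact would appear and could be recognized. The comparison of surgical with non-surgical subjects is also exposed, because surgical baselines are central: a laboratory offset could be read as a difference between populations. SAP 9.5 does advise care with the subgroup results, but because of population differences and small numbers, not because of the laboratory switch.

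**Working it through.** **The plan's own figure.** The plan gives no figure for this point. Its one calculation, the sample-size statement, reproduces: 1 − 0.99^250 = 0.919 (stated 92%) and 1 − 0.98^250 = 0.994 (stated 99%). It does not depend on the laboratory used.

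**Step 1: which laboratory supplies the baseline.** Non-surgical screening takes place on Day 1 before dosing. Table 3-3 schedules one set of safety laboratory tests in that period, and they are local. Earlier results from the facility, where accepted for eligibility, are local too. Under SAP 9.1 the local value is therefore the baseline.

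**Step 2: which laboratory supplies the later values.** None of the exceptions in Protocol 11.5.2 covers scheduled post-dose samples, so these are central. Table 3-4 schedules chemistry, hematology and coagulation at discharge (for non-surgical subjects only if admitted), at Day 14 or the End of Dosing Visit, and at follow-up only if a clinical finding requires it. Day 7 has none. A non-surgical subject who is not admitted therefore contributes one routine pair, local to central.

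**Step 3: surgical subjects.** Their screening samples are central, apart from a possible local repeat after a laboratory error. Their pairs are almost all central to central.

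**Step 4: which outputs use the baseline.**

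| Output | Uses baseline | Affected |
|---|---|---|
| Change from baseline, all subjects | Yes | Yes, at any non-surgical share |
| Change from baseline, non-surgical | Yes | Yes, if produced (at least 10%: 0.10 × 250 = 25 subjects) |
| Change from baseline, surgical | Yes | Hardly |
| Chemistry shifts, absolute cut-offs (albumin at 30 and 20 g/L) | Yes | Yes |
| Chemistry shifts, multiples of ULN | Yes | Partly protected if each result uses its own laboratory's ULN; the SAP does not say so |
| Threshold counts in the treatment-emergent period, including hemoglobin and platelets | No | No |

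**Step 5: size.** Two inputs are assumptions, because the documents give neither: b, the central-minus-local offset as a percentage of the value, and f, the non-surgical share of subjects contributing a pair at the visit. For a non-surgical subject, observed change = true change + b. With a common b, the non-surgical mean shifts by b and the all-subject mean by f × b.

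| f | b = 2% | b = 5% | b = 10% |
|---|---|---|---|
| 5% | 0.1% | 0.25% | 0.5% |
| 10% | 0.2% | 0.5% | 1.0% |
| 30% | 0.6% | 1.5% | 3.0% |

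The range 0.5–3% runs from 0.10 × 5% to 0.30 × 10%. If local laboratories differ from the central one in different directions, the mean shift is smaller. In the extreme case, with half at +b and half at −b, it is 0.5b − 0.5b = 0, but the spread of individual changes is wider.

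**The case against.** The strongest reply is that much of this is contained already. SAP 9.5 requires every safety summary for surgical subjects without condition, so a nearly all-central change table will exist beside the pooled one. All analyses are descriptive, so no error rate is involved. In a single-arm study, change from baseline does not isolate a drug effect anyway, because injury, recovery and rescue medication also move laboratory values. The offset is assumed, and nothing in the documents shows that a pooled shift of 0.5–3% would alter a safety reading. All of this stands and keeps the point minor. It does not remove the offset from the pooled and non-surgical tables, and nothing in the SAP tells the reader that it may be there.

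A reader might infer more than the documents support:

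- *That hemoglobin and platelet thresholds are distorted.* They are not. Threshold counts use treatment-emergent values, which are central when scheduled. None of the laboratory criteria in Table 12-3 has a change-from-baseline term, and the shift tables cover chemistry only. Albumin is reached through the shift table, not through the count.
- *That every later value is central.* This holds for scheduled samples only. Protocol 11.5.2 allows local tests for urgent medical issues.
- *That a non-surgical table is certain.* It appears only if the group reaches 10% of subjects. Below that, these subjects are listed separately but still enter the pooled summaries.
- *That the subtraction is certain to occur.* The documents do not say whether local results enter the analysis database. If they do not, these subjects have no scheduled laboratory baseline, which the SAP does not address either.

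**Conclusion.** The point holds as a minor one. As written, the plan lets a between-laboratory offset into the pooled change-from-baseline table, into the non-surgical table where that is produced, and into chemistry shifts with absolute cut-offs. Post-baseline threshold counts are untouched.

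The size cannot be set from the documents. It rests on an assumed common offset of 5–10%, which appears in full in the non-surgical mean, and an assumed non-surgical share of 10–30%, which gives 0.5–3% in the pooled mean. Offsets of differing sign would reduce both. The documents do not support reading this as a false safety signal; they show only that such an offset could not be told apart from a change on treatment. It also assumes that local results are entered in the database. Neither the sample size nor any stated probability changes.

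**What to change.** In SAP 9.4.2:

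1. Base the pooled absolute change-from-baseline summary on central-to-central pairs. In practice this is close to the surgical table already planned.
2. For non-surgical subjects, add low/normal/high shift tables for chemistry, hematology and coagulation, classifying each result by the reference range of the laboratory that produced it.
3. Keep any non-surgical absolute change table separate, with a footnote that baseline is local and post-baseline central.

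The SAP should also state that local screening results and their reference ranges are held in the database, because item 2 depends on it.

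Low/normal/high shifts suit this better than value/ULN alone, which is a poor scale for analytes where both directions matter, such as sodium or potassium. They are not a full correction, since reference limits need not track calibration differences. Keeping a footnoted absolute table avoids discarding almost all non-surgical change data.

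The cost is SAP wording, one extra table variant, and no non-surgical contribution to the pooled absolute change figure. No extra blood draw is needed and eligibility is unchanged.

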11.5.3 Physical Examinations and Vital Signs

A PE of all body systems and vital signs assessment will be performed at screening and select study visits. At other visits, symptom-directed PEs and symptom-directed vital signs assessments

can be performed at the discretion of the investigator or healthcare provider. If the Screening Visit occurs via home health (surgical subjects only), an abbreviated PE will be performed at screening and a complete PE will be performed on Day 1.

A PE includes a review of the following systems: head, neck, and thyroid; eyes, ears, nose, and throat (EENT); respiratory; cardiovascular; lymph nodes; abdomen; skin; musculoskeletal; and neurological. Breast, anorectal, and genital examinations will be performed when medically indicated. After screening, any clinically significant abnormal findings in PEs will be reported as AEs.

The abbreviated PE will include an assessment of the following body systems: general; cardiovascular system; respiratory system; skin; and abdomen.

A focused PE of the operative site (surgical subjects only) will be performed in order to assess wound healing.

Vital signs include blood pressure (systolic and diastolic), temperature, pulse rate, respiration rate, and oxygen saturation (SpO₂). The subject will be instructed to rest (seated or supine) for at least 5 minutes before vital signs are assessed.

If there is an abnormal clinical assessment during a home visit, depending on its severity and at investigator discretion, the subject may be instructed to have a PE or other evaluation in the clinic.

